12.7. Appendix 7: Anaphylaxis Criteria

Hypersensitivity reactions will be monitored using the diagnostic criteria for anaphylaxis as outlined by the Joint NIAID/FAAN Second Symposium on Anaphylaxis [Sampson, 2006]. The criteria do not make a distinction based on underlying mechanism. These criteria are summarized as follows:

1. Acute onset of an illness (minutes to several hours) with involvement of the skin, mucosal tissue, or both (e.g., generalized hives, pruritus or flushing, swollen lips-tongue-uvula), and at least one of the following:
 - Respiratory compromise (e.g., dyspnea, wheeze-bronchospasm, stridor, reduced peak expiratory flow [PEF], hypoxemia)
 - Reduced blood pressure (BP) or associated symptoms of end-organ dysfunction (e.g., hypotonia [collapse], syncope, incontinence)
2. Two or more of the following that occur rapidly after exposure to a likely allergen for that patient (minutes to several hours):
 - Involvement of the skin-mucosal tissue (e.g., generalized hives, itch-flush, swollen lips-tongue-uvula)
 - Respiratory compromise (e.g., dyspnea, wheeze-bronchospasm, stridor, reduced PEF, hypoxemia)
 - Reduced BP or associated symptoms (e.g., hypotonia [collapse], syncope, incontinence)
 - Persistent gastrointestinal symptoms (e.g., crampy abdominal pain, vomiting)
3. Reduced BP after exposure to known allergen for that patient (minutes to several hours):
 - Infants and children: low systolic BP (age specific) or greater than 30% decrease in systolic BP
 - Adults: systolic BP of less than 90 mm Hg or greater than 30% decrease from that person's baseline.

12.8. Appendix 8: Classification of Heart Failure

Physicians usually classify patients' heart failure according to the severity of their symptoms [[American Heart Association](#), 2014]. The table below describes the most commonly used classification system, the NYHA Functional Classification. It places patients in one of four categories based on how much they are limited during physical activity.

Class	Functional Capacity: How a patient with cardiac disease feels during physical activity
I	Patients with cardiac disease but resulting in no limitation of physical activity. Ordinary physical activity does not cause undue fatigue, palpitation, dyspnea or anginal pain.
II	Patients with cardiac disease resulting in slight limitation of physical activity. They are comfortable at rest. Ordinary physical activity results in fatigue, palpitation, dyspnea or anginal pain.
III	Patients with cardiac disease resulting in marked limitation of physical activity. They are comfortable at rest. Less than ordinary activity causes fatigue, palpitation, dyspnea or anginal pain.
IV	Patients with cardiac disease resulting in inability to carry on any physical activity without discomfort. Symptoms of heart failure or the anginal syndrome may be present even at rest.

Class	Objective assessment
A	No objective evidence of cardiovascular disease. No symptoms and no limitation in ordinary physical activity.
B	Objective evidence of minimal cardiovascular disease. Mild symptoms and slight limitation during ordinary activity. Comfortable at rest.
C	Objective evidence of moderately severe cardiovascular disease. Marked limitation in activity due to symptoms, even during less-than-ordinary activity. Comfortable only at rest.
D	Objective evidence of severe cardiovascular disease. Severe limitations. Experiences symptoms even while at rest.

For Example:

- A patient with minimal or no symptoms but a large pressure gradient across the aortic valve or severe obstruction of the left main coronary artery is classified: Function Capacity I, Objective Assessment D.
- A patient with severe anginal syndrome but angiographically normal coronary arteries is classified: Functional Capacity IV, Objective Assessment A.

12.9. Appendix 9: Definition of Cardiovascular Events

Cardiovascular Events (CV) Definition:

Investigators will be required to fill out the specific CV event page of the CRF for the following AEs and SAEs:

- Myocardial infarction/unstable angina
- Congestive heart failure
- Arrhythmias
- Valvulopathy
- Pulmonary hypertension
- Cerebrovascular events/stroke and transient ischemic attack
- Peripheral arterial thromboembolism
- Deep venous thrombosis/pulmonary embolism
- Revascularization

12.10. Appendix 10: Protocol Amendment History

The Protocol Amendment Summary of Changes Table for the current amendment is located directly before the Table of Contents (TOC).

Information regarding the previous amendment is as follows:

Amendment 01 13-JAN-2017

Overall Rationale for the Amendment: To provide the correct EudraCT number in the protocol.

Section # and Name	Description of Change	Brief Rationale
Title Page	Regulatory Agency Identifying Number: EudraCT# was changed from 2014-001232-11 to 2017-000184-32.	The change was made to reflect the correct EudraCT# associated with the protocol.

Numbering of Global Protocol Amendments

Type of Protocol Amendment	Numbering	Type of changes
Global	Amendment 02	New changes for all
Global	Amendment 01	New changes for all

Document History Table for Global Protocol Amendment

DOCUMENT HISTORY	
Document	Date of Issue
Amendment 02	16-Nov-2017
Amendment 01	13-Jan-2017
Original Protocol	02-Nov-2016

1. INTRODUCTION

The purpose of this reporting and analysis plan (RAP) is to describe the analyses to be included in the Clinical Study Report for Protocol 205203:

Protocol Revision Chronology:		
2016N289833_00	02-NOV-2016	Original
2016N289833_01	13-JAN-2017	Protocol Amendment 1: A change to the EudraCT# was made to reflect the correct EudraCT# associated with the protocol.
2016N289833_02	16-Nov-2017	Protocol Amendment 2: Optional biomarker sub-study has been added. The text was updated considering that investigators may adjust the participants' background HES therapy per standard of care starting at Visit 2. GSK tracking numbers were replaced with the term 'mepolizumab HES expanded access'.

2. SUMMARY OF KEY PROTOCOL INFORMATION

2.1. Study Objective(s) and Endpoint(s)

Objectives	Endpoints
Primary Objectives	Primary Endpoints

 To describe the long-term safety profile of mepolizumab in participants with HES who took part in Study 200622. 	
Primary
 
 Adverse events (AEs) [serious and non-serious] Anti-drug antibody 
Other Safety
 
 Vital signs 12-lead ECG Hematological and clinical laboratory tests
Exploratory Objectives	Exploratory Endpoints

 To assess the effect of long-term use of mepolizumab on multiple clinical outcomes. 	
 Rate of HES flare Change in the mean daily OCS dose from Weeks 0-4 to Weeks 16-20 Proportion of participants who achieve a mean daily OCS (prednisone/prednisolone or equivalent) dose of ≤ 7.5mg during Weeks 16-20

 To assess the effect of long-term use of mepolizumab on a PD marker 	
 Blood eosinophil levels

2.2. Study Design

Overview of Study Design and Key Features	

↑: Mepolizumab treatment (300mg SC per administration) V: Visit ^: Participants who continue with mepolizumab treatment via MHE104317/MHE112562 after Study 205203 will have the last assessment on Week 20 (Visit 6). #: Participants who do not continue with mepolizumab via MHE104317/MHE112562 after Study 205203 will have additional follow-up 12 weeks after the last dose (Visit 7).
	
Design Features	
 Multi-centre, open-label extension, 20-week treatment period, safety study of mepolizumab in adolescent and adult participants with HES who took part in the phase 3 study 200622. Visit 1 for study 205203 is the exit visit (32 weeks after randomisation) for study 200622. Investigators will be blinded to the blood eosinophil count from the sample obtained at visit 1 (first dosing visit), in order to maintain the blinding of study 200622, after which eosinophil counts will be unblinded starting from visit 2. Investigators may adjust the participants' background HES therapy per standard of care starting at visit 2 (approximately 4 weeks after the first dose of open-label mepolizumab). Participants who withdraw from study treatment prematurely should continue in the study per protocol until 20 weeks from first dose of open-label mepolizumab. Participants who complete assessments at visit 6 (week 20) may continue with mepolizumab treatment via MHE104317/MHE112562, where local regulation permits. Study participants who do not continue with MHE104317/MHE112562 will have an additional follow-up assessment 12 weeks after the last dose of mepolizumab.
Dosing	
 300 mg SC mepolizumab every 4 weeks (5 administrations) while continuing their HES therapy. The final dose of study treatment will be administered at Visit 5 (Week 16) with completion of the study treatment period achieved at the next 4-weekly visit.

Overview of Study Design and Key Features	
Time & Events	
 See Appendix 1: Schedule of Activities
Treatment Assignment	
 All participants are assigned to 300mg SC mepolizumab. Between 80 and 120 participants will be randomised in study 200622. Those participants who complete required assessments for 32 weeks starting from randomisation may be evaluated for eligibility to study 205203.
Interim Analysis	
 An external Independent Data Monitoring Committee (IDMC) will review ongoing data from study 205203 as potential supporting data for the overall assessment of safety for use of mepolizumab in the 200622 study population. The safety data analyses for the IDMC reviews will be performed by an independent statistical analysis data centre (SDAC). The IDMC will not issue recommendations for the conduct of study 205203. No other interim analysis is planned.
Main subject entry criteria	
 Study 200622 participants who meet one of the following criteria: 
 i. Completion of the 32-week treatment period in study 200622 ii. Participants withdrawn from study treatment prematurely during the 200622 study, but continue in the study per protocol until 32 weeks from randomisation.

2.3. Statistical Hypotheses / Statistical Analyses

No formal statistical hypothesis testing is planned.

2.4. Changes to the Protocol Defined Statistical Analysis Plan

- More detail was added to the protocol defined endpoint, change in mean daily OCS dose from Weeks 0-4 to Weeks 16-20. This additionally includes the change in mean daily OCS dose from Weeks 0-4 to Weeks 4-8, Weeks 8-12 and Weeks 12-16.
- An additional endpoint of the proportion of patients who achieve a mean daily OCS (prednisone/prednisolone or equivalent) dose reduction of 50% or more from Week 0-4 to Week 16-20 will be reported, for those subjects with a mean OCS dose during Week 0-4 greater than 0mg.

3. PLANNED ANALYSES

3.1. Interim Analyses

- An external Independent Data Monitoring Committee (IDMC) will periodically review unblinded safety data from study 200622, in accordance with the IDMC Charter. Data from study 205203 will also be provided for information to the IDMC as potential supporting data for the overall assessment of safety for use of mepolizumab in the 200622 study population. The safety data analyses for the IDMC reviews will be performed by an independent statistical analysis data centre (SDAC). The IDMC will not issue recommendations for the conduct of study 205203. GSK will evaluate if IDMC recommendations from study 200622 will require changes to study 205203.
- No other interim analysis is planned for this study.

3.2. Final Analyses

The final planned primary analyses will be performed after the completion of the following sequential steps:

1. All participants have completed the study as defined in the protocol.
2. All required database cleaning activities have been completed and final database release (DBR) and database freeze (DBF) has been declared by Data Management.

4. ANALYSIS POPULATIONS

Population	Definition / Criteria	Analyses Evaluated
All Participants Enrolled	
 All participants who sign the ICF and for whom a record exists on the data base 	
 Screen failures
Safety	
 All participants who received at least one dose of open-label mepolizumab. 	
 Safety Efficacy
Pharmacodynamic (PD)	
 All screened participants who had a baseline blood eosinophil measurement and at least one post-treatment eosinophil measurement. 	
 Blood eosinophils

Refer to [Appendix 8](#): List of Data Displays which details the population used for each display.

4.1. Protocol Deviations

Important protocol deviations (including deviations related to study inclusion/exclusion criteria, conduct of the trial, patient management or patient assessment) will be summarised and listed.

Protocol deviations will be tracked by the study team throughout the conduct of the study in accordance with the Protocol Deviation Management Plan (PDMP).

- Data will be reviewed prior to freezing the database to ensure all important deviations are captured and categorised on the protocol deviations dataset.
- This dataset will be the basis for the summaries and listings of protocol deviations.

A separate summary and listing of all inclusion/exclusion criteria deviations will also be provided. This summary will be based on data as recorded on the inclusion/exclusion page of the electronic case report form (eCRF).

5. CONSIDERATIONS FOR DATA ANALYSES AND DATA HANDLING CONVENTIONS

5.1. Study Treatment & Sub-group Display Descriptors

Summaries will be presented by the actual treatment the participant received in the randomised double-blind study (200622). With the exception of pharmacokinetic and pharmacodynamic data, summaries will also be presented for all subjects receiving open-label mepolizumab.

Treatment group descriptors will be assigned as follows:

Treatment Group Descriptions			
RandAll NG from Study 200622		Data Displays for Reporting	
Code	Description	Description	Order ^[1]
P	Placebo	300mg SC Prev. Placebo	1
A	Mepolizumab 300mg SC	300mg SC Prev. Mepo	2
N/A	N/A	300mg SC Total	3

NOTES:

- Order of treatments presented in Tables, Figures and Listings (TFLs), as appropriate.

5.2. Baseline Definitions

- Baseline will be defined as the latest assessment prior to open-label mepolizumab with a non-missing value, including those from unscheduled visits. If time is not collected, visit 1 assessments are assumed to be taken prior to first dose of open-label mepolizumab and used as the baseline.
- Where the exit visit for study 200622 (32 weeks post randomisation) is performed on the same day as visit 1 for study 205203, clinical safety laboratory assessments (including PD assessment of blood eosinophils), PK, immunogenicity and vital signs may not be repeated as part of visit 1 for study 205203. In these cases, the assessments at the exit visit for study 200622 will be defined as the baseline for study 205203 and will be transferred from the 200622 SDTM data sets to the Analysis Data Model (ADaM) reporting data sets for study 205203.
- In order to allow appropriate central ECG monitoring throughout the 205203 study, sites will be requested to conduct an ECG assessment prior to the first dose of open-label mepolizumab at visit 1 of study 205203, even if an ECG assessment was done on the same day as part of the exit visit for study 200622. The visit 1 ECG in study 205203 will be defined as the baseline. If more than one ECG is performed prior to open-label mepolizumab as part of visit 1 in study 205203, for each ECG parameter the mean of the available pre-dose values on the date of visit 1 in study 205203 will be assigned as the baseline value for that parameter. Additional ECGs on the date of visit 1 will be captured as unscheduled assessments with the same date as visit 1 in the clinical study data base; all visit 1 and unscheduled visits occurring prior to open-

label mepolizumab on the date of visit 1 in study 205203 will be considered to derive the baseline value.

5.3. Multicentre Studies

- In this multicentre global study, enrolment will be presented by investigative site and country.
- The following regions will be defined with consideration for standard of care medical practice. These regions correspond to the strata used for randomisation in study 200622.
 - USA
 - Argentina, Mexico and Brazil
 - Rest of World

5.4. Examination of Covariates, Other Strata and Subgroups

5.4.1. Covariates and Other Strata

- Where adjusted flare rates are presented (see Section 9.1.1.4), estimates will be adjusted for region and for baseline oral prednisone equivalent daily dose from study 200622.

5.4.2. Examination of Subgroups

No subgroup analyses will be performed.

5.5. Multiple Comparisons and Multiplicity

Analysis of the study data will be descriptive. No adjustment for multiplicity will be made.

5.6. Other Considerations for Data Analyses and Data Handling Conventions

Other considerations for data analyses and data handling conventions are outlined in the appendices:

Section	Component
13.1	Appendix 1: Schedule of Activities
13.2	Appendix 2: Study Phases and Treatment Emergent Adverse Events
13.3	Appendix 3: Data Display Standards & Handling Conventions
13.4	Appendix 4: Derived and Transformed Data
13.5	Appendix 5: Reporting Standards for Missing Data
13.6	Appendix 6: Values of Potential Clinical Importance

6. STUDY POPULATION ANALYSES

6.1. Overview of Planned Study Population Analyses

The study population analyses will be based on the Safety population, unless otherwise specified.

Study population analyses including analyses of subject's disposition, protocol deviations, demographic and baseline characteristics, prior and concomitant medications, and exposure and treatment compliance will be based on GSK Core Data Standards. Details of the planned displays are presented in [Appendix 8: List of Data Displays](#).

7. SAFETY ANALYSES

The safety analyses will be based on the Safety population, unless otherwise specified.

7.1. Adverse Events Analyses

Adverse events analyses including the analysis of adverse events (AEs), Serious (SAEs) and other significant AEs will be based on GSK Core Data Standards. The details of the planned displays are provided in [Appendix 8: List of Data Displays](#).

A summary of AEs reported by highest post-baseline binding antibody result (as defined in Section 8.1) will be produced.

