	
placebo (8% vs. 3%). There have been no reports of severe reactions. Pain, erythema, swelling, itching, and burning sensation were the most common symptoms reported.
 
 Local injection site reactions reported to date across the mepolizumab program are summarized in the Adverse Events of Special Interest' section of the IB; see also 'Section 6 titled 'Summary of Data and Guidance for the Investigator'. 	
study team and/or GSK safety review team.
 
 Customized AE and SAE case report form (CRF) will be utilized for targeted collection of systemic reactions data.
Potential risk of immunogenicity	
 Biopharmaceutical products may elicit anti-drug antibody (ADA) and neutralizing antibodies (NAB), which have the potential to modulate pharmacokinetics (PK), pharmacodynamics (PD) or produce adverse reactions. However, humanized and fully human antibodies are less immunogenic than mouse or chimeric monoclonal antibodies. In the placebo controlled severe asthma studies low incidence (6% 100 mg SC and 2% all IV doses) and low titer of ADA and neutralizing antibodies have been reported. To date there have been no apparent association with adverse events, loss of disease control and/or markedly altered PK or PD profiles associated with anti-mepolizumab antibodies in any participants. 
Immunogenicity data reported to date across the mepolizumab development program are summarized in the IB; see Section 5.4. 'Clinical Immunogenicity'
	
To characterize the potential risk of immunogenicity:
 
 Blood samples are collected in clinical studies for detection of both ADA and NAB. For participants who develop anti-mepolizumab antibodies systematic review of AE/SAE data at the end of the study will be conducted.

Potential Risk of Clinical Significance	Summary of Data/Rationale for Risk	Mitigation Strategy
	and a summary of immunogenicity findings in the 'Other Potentially Clinically Relevant Information for the Investigator' section located in Section 6 titled 'Summary of Data and Guidance for the Investigator'.	

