8.1. Overview of Immunogenicity Analyses

For the immunogenicity assessment, two types of anti-drug antibody (ADA) assays will be performed, a binding anti-drug antibody assay and a neutralizing antibody assay.

For the binding assay, there will be a three tiered analysis: screening, confirmation and titration. The screening assay produces a result of positive or negative relative to a screening cut point. Positive samples continue with the confirmation assay, which also produces a result of positive or negative relative to a confirmation cut point. For positive confirmation samples, a titre value will also be obtained to quantify the degree of binding in a titration assay and the sample will be tested with the neutralizing assay, which also reports results as positive or negative.

The binding ADA assay results at each visit will be summarised negative or positive. In addition, the highest post-baseline binding ADA assay confirmatory result obtained for a subject will be summarised. Subjects with both positive and negative results will be identified in the positive category. Summary statistics for the titre result by visit will also be presented.

A summary of adverse events by highest post-baseline binding ADA assay confirmatory result (as defined above) will be produced.

A summary of treatment emergent positive confirmatory binding ADA assay results in the subset of subjects who did not have a positive confirmatory binding ADA assay result prior to the dosing of study treatment will also be presented.

Neutralizing antibody assay results will be summarised by visit. In addition, the highest post-baseline neutralising antibody assay result during the treatment period of the study will be summarised, with subjects with both positive and negative results identified in the positive category.

Immunogenicity data will be listed for subjects with at least one positive screening binding assay result.

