13. APPENDICES

13.1. Appendix 1: Schedule of Activities

13.1.1. Protocol Defined Schedule of Events

Procedure Study Visit	Screening/Baseline 1	20-Week Treatment Period					WD (4 weeks post-last dose) ± 1 wk	Study Visit 7 Additional follow-up (12 weeks post-last dose ± 1 wk)	Flare	Notes
		2	3	4	5	6				
Study Weeks	0	4 ± 1 wk	8 ± 1 wk	12 ± 1 wk	16 ± 1 wk	20 ± 1 wk				
Informed consent	X									
Inclusion and exclusion criteria	X									
Demography	X									
Full physical examination including height and weight	X									
Past and current medical conditions	X									
Urine pregnancy test (WOCBP only) – serum test if locally required	X	X	X	X	X	X	X	X		Test is required for WOCBP on study treatment until the last follow-up.
Clinical safety laboratory assessments (include liver chemistries)	1	2	2	2	2	1	1		2	1: Hematology, chemistry, aldolase, troponin, urinalysis 2: Hematology, chemistry, aldolase, troponin
PK	X					X	X	X		
Immunogenicity (Anti-drug antibody)	X					X	X	X		
12-lead ECG	X					X	X			

Procedure	Screening/Baseline	20-Week Treatment Period					WD (4 weeks post-last dose) ± 1 wk	Study Visit 7 Additional follow-up (12 weeks post-last dose ± 1 wk)	Flare	Notes
		2	3	4	5	6				
Study Visit	1									
Study Weeks	0	4 ± 1 wk	8 ± 1 wk	12 ± 1 wk	16 ± 1 wk	20 ± 1 wk				
Vital signs	X	X	X	X	X	X	X		X	
HES Core Assessments/HES flare details	X	X	X	X	X	X	X		X	
Study treatment	X	X	X	X	X					
AE review	X	X	X	X	X	X	X	X	X	
SAE review	X	X	X	X	X	X	X	X	X	
Concomitant medication review	X	X	X	X	X	X	X	X	X	

wk: week

- The baseline visit is the exit visit (32 weeks after randomization) for Study 200622. Assessments that are captured as part of the exit visit for Study 200622 do not have to be repeated. Information will be transferred accordingly.
- Biological sample collection (for clinical safety laboratory, PK, and immunogenicity) is done prior to administration of study treatment on dosing visits (Visits 1 2, 3, 4, 5) as specified in the SoA.
- WD: Prematurely discontinuation of mepolizumab (~4 weeks after the last dose of mepolizumab).
- Visit 7 - Additional follow-up is required 12 weeks after the last dose of mepolizumab for participants who do not continue with mepolizumab via MHE104317/MHE112562 at that time.

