13.8.5. Safety Tables

No.	Population	IDSL / Example Shell	Title	Programming Notes	Deliverable
Adverse Events					
2.1.	Safety	AE1	Summary of All On-Treatment Adverse Events by System Organ Class and Preferred Term		SAC
2.2.	Safety	AE1	Summary of All Post-Treatment Adverse Events by System Organ Class and Preferred Term		SAC
2.3.	Safety	AE3	Summary of Common ($\geq 3\%$ Incidence) On-Treatment Adverse Events by Overall Frequency		SAC
2.4.	Safety	AE15	Summary of Common ($\geq 3\%$ Incidence) On-Treatment Non-Serious Adverse Events by System Organ Class and Preferred Term (Number of Subjects and Occurrences)		SAC
2.5.	Safety	AE5A	Summary of All On-Treatment Adverse Events by Maximum Intensity by System Organ Class and Preferred Term		SAC
2.6.	Safety	AE1	Summary of All Drug-Related Adverse Events by System Organ Class and Preferred Term		SAC
2.7.	Safety	AE5A	Summary of All Drug-Related Adverse Events by Maximum Intensity by System Organ Class and Preferred Term		SAC
2.8.	Safety	AE1	Summary of Non-Serious Drug-Related Adverse Events by System Organ Class and Preferred Term		SAC
2.9.	Safety	AE1	Summary of On-Treatment Adverse Events by Highest Post-Baseline Binding Antibody Result	Add in row with n in each binding antibody result category.	SAC
2.10.	Safety	AE3	Summary of All Adverse Events Leading to Permanent Discontinuation from Study Treatment by Overall Frequency		SAC

CONFIDENTIAL

205203

No.	Population	IDSL / Example Shell	Title	Programming Notes	Deliverable
Adverse Events					
2.11.	Safety	AE3	Summary of All Adverse Events Leading to Withdrawal from the Study by Overall Frequency		SAC
2.12.	Safety	AE1	Summary of Adverse Events Reported on the Day of Dosing by System Organ Class and Preferred Term		SAC
2.13.	Safety	AE7	Listing of Subject Numbers for Individual On-Treatment Adverse Events		SAC
2.14.	Safety	AE7	Listing of Subject Numbers for Individual Post-Treatment Adverse Events		SAC
2.15.	Safety	AE2	Listing of Relationship of Adverse Event, System Organ Classes, Preferred Terms and Verbatim Text		SAC
Adverse Event Overview					
2.16.	Safety	SAFE_T1	Adverse Event Overview		SAC
Serious Adverse Events					
2.17.	Safety	AE3	Summary of Fatal Serious Adverse Events by Overall Frequency		SAC
2.18.	Safety	AE3	Summary of Drug-Related Fatal Serious Adverse Events by Overall Frequency		SAC
2.19.	Safety	AE3	Summary of Non-Fatal Serious Adverse Events by Overall Frequency		SAC
2.20.	Safety	AE3	Summary of All Serious Adverse Events by Overall Frequency		SAC

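### Table 2.9 groups adverse events by post-baseline antibody results only, so a participant positive at Visit 1 and negative at every later sample is shown as antibody-negative

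*SAP*

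**What the plan says.** SAP 7.1 plans one summary of adverse events by antibody status: "A summary of AEs reported by highest post-baseline binding antibody result (as defined in Section 8.1) will be produced". In the display list (SAP 13.8.5) this is Table 2.9, "Summary of On-Treatment Adverse Events by Highest Post-Baseline Binding Antibody Result".

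SAP 8.1 defines the grouping variable: "the highest post-baseline binding ADA assay confirmatory result obtained for a subject will be summarised". The next sentence settles mixed results: "Subjects with both positive and negative results will be identified in the positive category".

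SAP 5.2 defines baseline: "Baseline will be defined as the latest assessment prior to open-label mepolizumab with a non-missing value, including those from unscheduled visits". It names immunogenicity among the assessments that need not be repeated at Visit 1 when the Study 200622 exit visit falls on the same day. In that case "the assessments at the exit visit for study 200622 will be defined as the baseline for study 205203".

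The schedule (Protocol section 2; SAP 13.1.1) places antibody samples at Visit 1 before dosing, Visit 6 (Week 20), the withdrawal (WD) visit and Visit 7. None is scheduled at Weeks 4 to 16. Visit 7 applies only to participants who do not go on to expanded access.

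On the immunogenicity risk, Protocol 3.3.1 adds: "For participants who develop anti-mepolizumab antibodies systematic review of AE/SAE data at the end of the study will be conducted".

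**The concern.** Grouping by post-baseline result is natural when everyone starts drug-naive. Here, Study 200622 randomised 1:1, so about half of the entrants may already have had up to 32 weeks of mepolizumab. For them, Visit 1 is the only scheduled sample in this study that shows whether antibodies were present when open-label dosing began.

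The SAP recognises this group when it counts antibodies: Table 2.60 is restricted to participants with no positive result before dosing. It does not carry the distinction into the adverse event table.

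Adverse events and anti-drug antibody are the two primary endpoints, and Table 2.9 is the only planned adverse event table split by antibody status. The tables of systemic and injection-site reactions (2.26 to 2.35) are not split. Compared with a rule that also counts baseline, the SAP rule can only move people from positive to negative. If antibodies and events were related, that would tend to weaken the contrast.

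**Working it through.** The documents give no figure on this point, so there is nothing to reproduce. The check has two parts.

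**1. Which participants does the rule place differently?**

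Code each confirmed binding result as 1 (positive) or 0 (negative).

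- SAP rule: class = maximum over post-baseline results.
- Comparison rule: class = maximum over baseline and post-baseline results.

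Visit 1 (2 values), Week 20 (2 values) and Visit 7 (not taken, 0 or 1) give 2 × 2 × 3 = 12 patterns. The rules can differ only when Visit 1 is positive, which leaves six:

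| Visit 1 | Week 20 | Visit 7 | SAP rule | Counting baseline |
|---|---|---|---|---|
| + | − | not taken | negative | positive |
| + | − | − | negative | positive |
| + | − | + | positive | positive |
| + | + | not taken | positive | positive |
| + | + | − | positive | positive |
| + | + | + | positive | positive |

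Two of the 12 patterns change class. A WD or unscheduled post-baseline sample enters the maximum in the same way. The affected set is therefore: positive at Visit 1 and negative at every post-baseline sample taken.

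The mixed-results sentence in SAP 8.1 does not bring the Visit 1 result back in, because it directly follows and qualifies the post-baseline definition.

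Table 2.9 covers on-treatment events, from first dose to last dose plus 28 days (SAP 13.2.1). With the last dose at Week 16, that is 16 × 7 + 28 = 140 days, or Week 20. For a completer going to expanded access, all open-label events are thus classified by one scheduled sample at the end of that window.

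**2. How many people might this be?**

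Inputs:
- 80 to 120 randomised in Study 200622 (SAP 2.2) at 1:1 (Protocol 3.1), so 40 to 60 on mepolizumab. Full rollover is assumed.
- Antibody incidence of 2% (IV) and 6% (100 mg SC) from the severe asthma studies (Protocol 3.3.1). These are the only rates in the documents. Applying them to 300 mg SC in HES, and to status at Visit 1, is an assumption.

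Expected positive entrants = n × p; chance of at least one = 1 − (1 − p)^n:

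| n | p | Expected | Chance of at least one |
|---|---|---|---|
| 40 | 2% | 0.8 | 0.55 |
| 40 | 6% | 2.4 | 0.92 |
| 60 | 2% | 1.2 | 0.70 |
| 60 | 6% | 3.6 | 0.98 |

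The number misplaced is this count times r, the share negative at every later sample. The documents do not give r. Over its full range of 0 to 1, the expected number runs from 0 to 3.6. An arbitrary r of 25% to 75% gives 0.8 × 0.25 = 0.2 to 3.6 × 0.75 = 2.7.

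For comparison, the same rates applied to all participants give an antibody-positive column of 80 × 2% = 1.6 to 120 × 6% = 7.2 people. One person more or less would be visible in it.

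**The case against.** The strongest defence is that the rule is stated and usable, and that the Visit 1 result is reported elsewhere. It appears by visit in Table 2.59 and defines the subset in Table 2.60. Listing 32 covers anyone with a positive screening result, and adverse events are listed in full (Listing 12), with separate listings of systemic and local reactions (18 to 21). For a handful of people, a reader could link antibodies to events by hand. The protocol also promises an end-of-study review of events in participants who develop antibodies. The analysis is descriptive, with no hypothesis test (SAP 2.3). All of this stands and limits the harm, but none of it changes the split in Table 2.9.

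A second defence also stands in part. With no sample between Visit 1 and Week 20, status at each dose is unknown. Someone positive at Visit 1 may have been negative for most of the doses, so pooling all their events as antibody-positive could err in the other direction. This argues for a separate class rather than for leaving them among the negatives.

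The illustration is also generous. The asthma rates are incidences, so anyone who reverted before Visit 1 is not the case described. Rollover will not be complete. Protocol 6.2 excludes anyone with a history of hypersensitivity to a monoclonal antibody, and anyone permanently withdrawn from treatment in Study 200622 for a related event.

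A reader might infer stronger points that the documents do not support:
- That a negative Week 20 sample alone decides the class. A positive WD, Visit 7 or unscheduled post-baseline sample would place the participant in the positive group.
- That the Visit 1 result is ignored. It is reported, but not used to split adverse events.
- That these participants are already sensitised. A positive binding assay is not shown to mean that, and Protocol 3.3.1 reports no apparent link with adverse events so far.
- That PK Table 4.1 and the eosinophil plot have the same fault. There, immunogenicity status is simply undefined, so no error can be shown.

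**Conclusion.** The point holds in a limited form. Under SAP 5.2, 7.1 and 8.1, a participant confirmed positive at Visit 1 and negative at every post-baseline sample has all open-label adverse events shown as antibody-negative in Table 2.9. This follows from the definitions and needs no assumption.

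The size does need assumptions. It is unknown and probably small: 0.8 to 3.6 positive entrants if the asthma rates and full rollover applied, of whom an undocumented share would be later negative. The result may be nobody.

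It is still worth correcting, because the positive column is likely to hold only a few people and no other planned table links the two primary endpoints. A reader might go further and conclude that the study would report a false absence of association. The documents do not support that: no test or decision rule rests on Table 2.9, and the statement of no apparent association in Protocol 3.3.1 describes earlier data.

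**What to change.** In SAP 7.1, SAP 8.1 and Table 2.9, replace the two-way split with three mutually exclusive classes based on the confirmed binding result:

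1. positive at baseline (Visit 1, or the Study 200622 exit sample where that serves as baseline);
2. not positive at baseline, first positive after baseline;
3. never positive.

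This keeps participants who were positive on entry visible without pooling them with new positives or with negatives. Leave Tables 2.59 and 2.60 as they are.

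The cost is short wording changes in two SAP sections and the table specification, one derived flag from results already collected, and one more small row. No extra samples are needed. The baseline-positive class may hold very few people or none, and should be read case by case alongside Listing 32.
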